### 9.4.2 ANALYSIS OF THE PRIMARY ENDPOINT(S)

Longitudinally measured BIS scores will be modeled using linear mixed effects (LME) regression with the measures at each time point relative to baseline (denoted by  $\Delta$ ) as the response variable and fixed effects for experimental conditions (BRIGHT, AC), time (1-week, 1-month, and 3-months post intervention) and their interaction. Models will include subject-specific random effects to account for correlation among measures obtained from the same subject over time. We will use qq-plots and histograms to investigate the assumption of approximate normality and consider transformations (e.g., log) as needed. We will assess the functional form of time to account for any non-linear temporal trends and consider transformations as needed. Comparisons of the change from baseline to each time point between conditions will be performed using model-based linear contrasts. Data will be disaggregated by age, sex, and race to allow for analysis of each as biological variables.

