### 9.4.3 ANALYSIS OF THE SECONDARY ENDPOINT(S)

For secondary endpoints related to psychological, emotional, and social well-being, graphical displays such as scatterplots and boxplots will be constructed to demonstrate patterns of individual continuous measures and differences between baseline, 1-week, 1- and 3-months post intervention. Summary descriptive statistics (statistics (e.g. frequencies and percent for categorical variables, and mean, median, standard deviation, and range for continuous variables) will be reported. Longitudinal measures of psychological, social, and emotional well-being will be modeled using LME regression with the measures at each time point relative to baseline (denoted by  $\Delta$ ) as the response variable and fixed effects for experimental conditions (BRIGHT, AC), time (1-week, 1-month, and 3-months post intervention) and their interaction. Models will include subject-specific random effects to account for correlation among measures obtained from the same subject over time. We will use qq-plots and histograms to investigate the assumption of approximate normality and consider transformations (e.g., log) as needed. We will assess the functional form of time to account for any non-linear temporal trends and consider transformations as needed. Comparisons of the change from baseline to each time point between

conditions will be performed using model-based linear contrasts. Data will be disaggregated by age, sex, and race to allow for analysis of each as biological variables.

[figure not shown]

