To evaluate whether the effect of BRIGHT on change in BID at 1-month post-intervention is partially mediated by changes in body image coping behavior at 1-week post intervention, we will perform exploratory mediation analysis. The total effect of the intervention (path  $c$ ) will be partitioned into direct (path  $c'$ ) and indirect effects, which we will test for statistical significance (Fig. 5). We will examine the direct effect of the intervention on change in BID ( $\Delta$  in Body Image Scale score) the mediating effect of change in body image coping behavior ( $\Delta$  in Body Image Coping Strategies Inventory score) on change in BID, and the effect of the intervention on the mediator ( $\Delta$  in Body Image Coping Strategies Inventory score). If paths  $a$ ,  $b$ , and  $c$  are statistically significant and  $c'$  (the direct effect) is reduced compared with  $c$  (the total effect), then partial mediation criteria are satisfied. The significance of the mediating effect will be tested using robust bootstrapping. Bootstrapping is considered superior to other methods of analyzing indirect effects because bootstrapping provides confidence intervals based on the bootstrap distribution instead of simply p values. In situations with smaller samples and non-normal distributions, the bootstrapping method is more likely to achieve an unbiased estimate of the indirect effect than other methods. The confidence interval for the mediating effect will be provided from the bootstrap analysis with the 'robmed' R package. This analysis will be repeated for change in BID at 3-months post and change in image coping behavior at 1-month post-intervention. Plots of mediated effect will be made to investigate the distribution of data and improve understanding of the relations among the variables. LME regression will be considered to assess the three-way interaction (moderator-intervention-time) for age, sex and race.

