#### 9.4.7 SUB-GROUP ANALYSES

Planned sub-group analyses of the primary endpoint will occur based on age, race, and sex to evaluate the impact of inclusion across the lifespan, race, and sex as biologic variables.

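### The only moderator test named for age, sex and race is a three-way interaction which, with change scores as the response, misses any moderation that is equal at every visit

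*Combined protocol and SAP*

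**What the plan says.** - **Moderator test (9.4.3).** At the end of the exploratory mediation paragraph: "LME regression will be considered to assess the three-way interaction (moderator-intervention-time) for age, sex and race". The sentence does not restate the response variable or the time levels.
- **Response variable.** For the primary endpoint, 9.4.2 specifies "linear mixed effects (LME) regression with the measures at each time point relative to baseline". For the well-being endpoints, 9.4.3 says the longitudinal measures "will be modeled using LME regression with the measures at each time point relative to baseline".
- **Fixed and random effects (9.4.2, same structure in 9.4.3).** "fixed effects for experimental conditions (BRIGHT, AC), time (1-week, 1-month, and 3-months post intervention) and their interaction". Baseline is subtracted and is not a level of time. "Models will include subject-specific random effects to account for correlation among measures obtained from the same subject over time".
- **Other uses of age, sex and race.** 9.4.7: "Planned sub-group analyses of the primary endpoint will occur based on age, race, and sex". 9.4.2: "Data will be disaggregated by age, sex, and race to allow for analysis of each as biological variables". Neither names an interaction term, a contrast or a test.

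**The concern.** Moderator by arm by time is the usual moderation test when raw scores are modelled and baseline is one of the time levels. Here baseline has already been subtracted. The treatment effect is therefore the arm difference in change at each visit, and arm by time only describes how that effect varies between visits. The same holds one order up: moderation of the effect sits in arm by moderator at each visit, and the three-way term only describes how it varies between visits.

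The plan wants to know whether age, sex and race bear on the primary effect (9.4.7; 5.5.1 says the same of age and clinical impact). Section 9.2 says the results are to guide a larger trial. A non-significant three-way term could be read there as absence of moderation when the test had no ability to detect the simplest form of it.

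**Working it through.** **Algebra.** Let A be arm, M the moderator and t the visit. With change from baseline as the response, the saturated mean is

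E[Δ at t] = μ(t) + α(t)·A + β(t)·M + γ(t)·A·M, for t = 1 week, 1 month, 3 months.

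- The difference in BRIGHT effect between moderator groups at visit t is γ(t). For the primary endpoint the quantity of interest is γ(1 month).
- With 1 week as reference, the arm-by-moderator coefficient is γ(1 week). The two three-way coefficients are γ(1 month) − γ(1 week) and γ(3 months) − γ(1 week).
- The three-way null (2 df) is γ(1 week) = γ(1 month) = γ(3 months). If all three equal 4.4, the coefficients are 4.4, 0 and 0, so the null is true and the test rejects at alpha.
- The 1-month contrast is arm by moderator plus its 1-month component: γ(1 week) + [γ(1 month) − γ(1 week)] = γ(1 month).

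**Check in a fitted model.** One simulated data set was used, with 44 patients, 3 visits and a random intercept. A constant moderation of 0, 4.4 or 20 points was added. The three-way coefficients (−2.07, −1.74) and their Wald chi-square (0.4645) did not change. The arm-by-moderator coefficient moved from 4.4 to 8.8 to 24.4; the 4.4 at zero added moderation is sampling noise.

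**The plan's own figure.** Section 9.2 gives 80.2% power for 22 per arm, standardized effect 0.78 and two-sided alpha 0.10. A noncentral t with 42 df and noncentrality 0.78 × √(22/2) = 2.587 gives 81.6%, close to the stated value. The plan states no power for the moderator test.

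**Size of the gap.**

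- From 9.2: 22 per arm; pooled SD of change 5.62; assumed mean changes 4.6 and 0.2, so the whole assumed effect is 4.6 − 0.2 = 4.4 points.
- From 9.4.1: two-sided 0.05.
- Assumed, not in the documents: binary moderator with 11 patients per arm-by-moderator cell; SD 5.62 at every visit; within-patient correlation of change scores 0.3 to 0.7 (affects only the three-way simulation); no missing data.

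Standard error of the 1-month contrast: 5.62 × √(4/11) = 3.39. Power is from the noncentral t with 40 df:

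| Constant difference | Noncentrality | 1-month contrast | Three-way test |
|---|---|---|---|
| 4.4 | 4.4/3.39 = 1.30 | 24% | about 5% |
| 6 | 6/3.39 = 1.77 | 41% | about 5% |
| 8 | 8/3.39 = 2.36 | 63% | about 5% |

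The three-way column follows from the algebra. Simulation with a split-plot F test agrees: at 4.4 points it rejected in 4.4% to 5.1% of runs across the three correlations.

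Sensitivity:

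- At alpha 0.10, the level used in 9.2, the 4.4-point figures are about 10% (three-way) and 36% (1-month contrast).
- Pooling the two stated arm SDs equally gives √((5.9² + 3.9²)/2) = 5.00 instead of 5.62. The 1-month contrast then has about 30% power at 4.4 points. The three-way test does not change.

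**Race.** Table 5 in 5.5.1 plans 37 White, 6 African American and 1 Asian participant. Assume 19 and 18 White and 3 and 4 non-White by arm. The standard error is 5.62 × √(1/19 + 1/18 + 1/3 + 1/4) = 4.67, and power for 4.4 points is about 15%.

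**The case against.** Several points on the other side stand.

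- **The response variable is inferred.** The sentence in 9.4.3 does not say what is modelled. If raw scores with baseline as a time level were meant, the three-way term would be the right test. But both mixed-model specifications in 9.4 use change scores, as does the rest of that paragraph, so change is the natural reading. If raw scores were intended, the plan needs to say so.
- **The commitment is weak.** The model is only to be considered, and no objective in Section 3 or hypothesis in 9.1 concerns moderation of BIS change by age, sex or race. This limits the importance of the point, not its correctness.
- **The information is in the same fit.** A hierarchical three-way model contains arm by moderator. But the plan does not say to read it, and under reference coding that coefficient refers to whichever visit is the reference.
- **Exact constancy is the extreme case.** Moderation that varies between visits is partly detectable by the three-way test.
- **The replacement is also weak.** At 4.4 points the 1-month contrast misses about 76% of the time for an evenly split moderator, and more often for race. Differences of 6 and 8 points exceed the plan's whole assumed treatment effect. Still, the contrast gains power as the difference grows, and the three-way test does not.

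A reader might go further and infer that the plan would report no moderation despite strong sub-group differences, or that it cannot see such differences at all. The documents do not support either reading. No decision or reporting rule is attached to the three-way test, and the sub-group analyses in 9.4.7 could show a constant difference descriptively. The gap lies in the one test that is named.

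**Conclusion.** The point holds as a mismatch between the named moderator test and the model it would be fitted in. Given change from baseline as the response and three post-intervention visits, the blindness to constant moderation is a matter of algebra and needs no assumption about SD or correlation. The comparison at 4.4 points, about 5% against about 24%, does rest on SD 5.62, 11 per cell, complete data and alpha 0.05. The consequence is confined to an exploratory analysis: the primary comparison and the sample size are unaffected. With 44 patients, neither test can support a conclusion that moderation is absent.

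**What to change.** 1. **9.4.3:** name as the moderator analysis the arm-by-moderator contrast for BIS change at 1 month, from the same mixed model (arm by moderator plus its 1-month component). State that the response is change from baseline. Keep the three-way term only to describe whether moderation changes over time.
2. **9.4.7:** this section contains no three-way term, so nothing is replaced. Add a cross-reference so that sub-group estimates are accompanied by this contrast.
3. **Reporting:** give the contrast as an exploratory estimate with a confidence interval, with age continuous. State that power is low and that a non-significant result is not evidence of no moderation. Under the assumptions above, the 95% interval for an evenly split moderator would be about ±2.02 × 3.39 = ±6.8 points, wider than the whole assumed treatment effect.

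The cost is a few sentences of wording, with no new data and no change to the fitted model.

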#### 9.4.4 SAFETY ANALYSES

N/A

#### 9.4.5 BASELINE DESCRIPTIVE STATISTICS

**Fig. 5. Exploratory mediator analysis.** Changes in body image coping behavior (Mediator [M1]) are hypothesized to mediate the effect of the intervention (independent variable [IV]) on changes in body image disturbance (dependent variable [DV]).

Baseline characteristics (e.g., demographics, oncologic details, behavioral characteristics) for the BRIGHT and AC arms will be compared and descriptive statistics calculated. Baseline differences between the two groups will be compared using t-tests and chi-square tests, or Wilcoxon rank sum and Fisher's exact tests as appropriate.

#### 9.4.6 PLANNED INTERIM ANALYSES

N/A

#### 9.4.7 SUB-GROUP ANALYSES

Planned sub-group analyses of the primary endpoint will occur based on age, race, and sex to evaluate the impact of inclusion across the lifespan, race, and sex as biologic variables.

#### 9.4.8 TABULATION OF INDIVIDUAL PARTICIPANT DATA

Individual participant data will not be listed by measure and time point.

#### 9.4.9 EXPLORATORY ANALYSES

N/A

### 10 SUPPORTING DOCUMENTATION AND OPERATIONAL CONSIDERATIONS

#### 10.1 REGULATORY, ETHICAL, AND STUDY OVERSIGHT CONSIDERATIONS

##### 10.1.1 INFORMED CONSENT PROCESS

###### 10.1.1.1 CONSENT/ASSENT AND OTHER INFORMATIONAL DOCUMENTS PROVIDED TO PARTICIPANTS

Consent forms describing in detail the study intervention, study procedures, and risks will be provided to the participant (either on paper or electronically as an eConsent) and documentation of informed consent will be completed prior to starting the study intervention.

###### 10.1.1.2 CONSENT PROCEDURES AND DOCUMENTATION

We will obtain full written (either via paper-based or electronic signature) informed consent from patients enrolling in the study. Informed consent will occur via face-face discussion in clinic or via telemedicine between one of the study team members designated to perform informed consent and the potential study participant. The study member will explain the elements of the informed consent form including purpose, methods, extent of the study, risks, benefits, and alternatives to potential participants. Participants will be asked to read the consent form, given appropriate time to read the document on their own, and allowed to ask any questions prior to signing it. Consents will be written in simple, easy-to-understand language and obtained on the day of enrollment by one of the study team members designated to perform informed consent. A study team member will answer any questions about the

study and participants will be asked to sign the consent and HIPAA forms. All participants will sign informed consent forms before the interview (either via paper-based informed consent or electronic signature of the REDCap-based electronic informed consent). All participants will receive a copy of their informed consent and HIPAA forms for their records (either a paper copy or an emailed copy). The informed consent process will take place in a private room in the Rutledge Tower Head and Neck Cancer Clinic, in a private room in the HCC, or the location that the patient is conducting the telemedicine clinic visit in cases of electronic informed consent. Only the study participant will provide informed consent. Subjects will be allowed up to one week to decide whether to participate in the study. Participants will also complete a HIPAA form at the same time using the same procedures as described above. All participants will receive a copy of their informed consent and HIPAA forms (either paper or emailed) for their records. Separate copies of the documents will be stored in the study binder under each patient's section.

---

#### 10.1.2 STUDY DISCONTINUATION AND CLOSURE

This study may be temporarily suspended or prematurely terminated if there is sufficient reasonable cause. Written notification, documenting the reason for study suspension or termination, will be provided by the suspending or terminating party to study participants, investigator, funding agency, and regulatory authorities. If the study is prematurely terminated or suspended, the PI will promptly inform study participants, the IRB, and sponsor/funding agency and will provide the reason(s) for the termination or suspension. Study participants will be contacted, as applicable, and be informed of changes to study visit schedule.

Circumstances that may warrant termination or suspension include, but are not limited to:

- Determination of unexpected, significant, or unacceptable risk to participants
- Insufficient compliance of study staff to the protocol (e.g. significant protocol violations)
- Data that are not sufficiently complete and/or evaluable

The study may resume once concerns about safety, protocol compliance, and data quality are addressed, and satisfy the funding agency, sponsor, IRB, Food and Drug Administration (FDA), or other relevant regulatory or oversight bodies (OHRP, DSMB).

---

#### 10.1.3 CONFIDENTIALITY AND PRIVACY

Participant confidentiality and privacy is strictly held in trust by the participating investigators, their staff, the safety and oversight monitor(s), and the sponsor(s) and funding agency. This confidentiality is extended to the data being collected as part of this study. Data that could be used to identify a specific study participant will be held in strict confidence within the research team. No personally identifiable information from the study will be released to any unauthorized third party without prior written approval of the sponsor/funding agency. To help protect participant confidentiality, we will assign a unique study ID number to each subject's information in place of his/her name and will label data collection forms only with the ID number. All hard copy and electronic files will be stored appropriately using double-locked methods and password-protection. Only the study team member will have access to study records. Participant data will be collected and recorded on either a password-protected electronic data capture format (Research Electronic Data Capture; REDCap) or paper-based forms depending upon patient

preference. For the paper collection data method, the data collection form will be labeled only with the participant's unique study ID number, and then stored within locked drawers in a locked office. The information on these paper forms will be transferred to a password-protected REDCap database such that all data will be stored in the password-protected REDCap Database. Only members of the study team will have access to the data. We have no plan to use laptops, jump drives, CDs/DVDs to transport data.

All research activities will be conducted in as private a setting as possible.

The study monitor, other authorized representatives of the sponsor or funding agency, representatives of the IRB, regulatory agencies or representatives from companies or organizations supplying the product, may inspect all documents and records required to be maintained by the investigator, including but not limited to, medical records (office, clinic, or hospital) and pharmacy records for the participants in this study. The clinical study site will permit access to such records.

The study participant's contact information will be securely stored at each clinical site for internal use during the study. At the end of the study, all records will continue to be kept in a secure location for as long a period as dictated by the reviewing IRB, Institutional policies, or sponsor/funding agency requirements.

It is NIH policy that the results and accomplishments of the activities that it funds should be made available to the public (see <https://grants.nih.gov/policy/sharing.htm>). The PI will ensure all mechanisms used to share data will include proper plans and safeguards for the protection of privacy, confidentiality, and security for data dissemination and reuse (e.g., all data will be thoroughly de-identified and will not be traceable to a specific study participant). Plans for archiving and long-term preservation of the data will be implemented, as appropriate.

To further protect the privacy of study participants, the Secretary, Health and Human Services (HHS), has issued a Certificate of Confidentiality (CoC) to all researchers engaged in biomedical, behavioral, clinical or other human subjects research funded wholly or in part by the federal government. Recipients of NIH funding for human subjects research are required to protect identifiable research information from forced disclosure per the terms of the NIH Policy (see <https://humansubjects.nih.gov/coc/index>). As set forth in 45 CFR Part 75.303(a) and NIHGPS Chapter 8.3, recipients conducting NIH-supported research covered by this Policy are required to establish and maintain effective internal controls (e.g., policies and procedures) that provide reasonable assurance that the award is managed in compliance with Federal statutes, regulations, and the terms and conditions of award. It is the NIH policy that investigators and others who have access to research records will not disclose identifying information except when the participant consents or in certain instances when federal, state, or local law or regulation requires disclosure. NIH expects investigators to inform research participants of the protections and the limits to protections provided by a Certificate issued by this Policy.

---

#### 10.1.4 FUTURE USE OF STORED SPECIMENS AND DATA

Data collected for this study will be analyzed and stored with the study team. After the study is completed, the de-identified, archived data will be transmitted to and stored with the study team, for use by other researchers including those outside of the study.

---

#### 10.1.6 SAFETY OVERSIGHT

Safety oversight will be under the direction of a PI. Aggregate reviews will occur by the PI for all AEs, UPs, protocol violations, audit results, early withdrawals, whether the study accrual pattern warrants continuation/action, and endpoint data. Aggregate reviews will occur monthly.

#### 10.1.7 CLINICAL MONITORING

N/A

#### 10.1.8 QUALITY ASSURANCE AND QUALITY CONTROL

Each clinical site will perform internal quality management of study conduct, data and biological specimen collection, documentation and completion.

Quality control (QC) procedures will be implemented as follows:

**Informed consent** --- Study staff will review both the documentation of the consenting process as well as a percentage of the completed consent documents. This review will evaluate compliance with GCP, accuracy, and completeness. Feedback will be provided to the study team to ensure proper consenting procedures are followed.

**Source documents and the electronic data** --- Data will be initially captured on source documents (see **Section 10.1.9, Data Handling and Record Keeping**) and will ultimately be entered into the study database. To ensure accuracy site staff will compare a representative sample of source data against the database, targeting key data points in that review.

**Intervention Fidelity** — Consistent delivery of the study interventions will be monitored throughout the intervention phase of the study. Procedures for ensuring fidelity of intervention delivery are described in **Section 6.2.1, Interventionist Training and Tracking**.

Should independent monitoring become necessary, the PI will provide direct access to all trial related sites, source data/documents, and reports for the purpose of monitoring and auditing by the sponsor/funding agency, and inspection by local and regulatory authorities.

